4.1.2 Method of assigning subjects to treatment groups

The allocation of subjects to study subject numbers will be performed prior to the first administration of trial medication in the morning of Day 1 (Visit 2). For this purpose, the subjects will be allocated to a study subject number by drawing lots.

Once a subject number has been assigned, it cannot be reassigned to any other subject.

4.1.3 Selection of doses in the trial

The oral dose of 50 mg BI 409306 was selected since it is expected to be a therapeutic dose and was well tolerated in previous studies (section 1.2).

Using the microtracer approach for investigating the absolute bioavailability the intravenous dose should not significantly add to the systemic drug concentrations arising from the oral administration [R17-1799].

The oral dose (50 mg BI 409306) is 500 times higher than the intravenously infused dose (0.1 mg BI 409306 [C-13/N-15]). Therefore the exposure to BI 409306 (C-13/N-15) originating from the infused microdose is considered negligible (see section 2.3).

With the bioanalytical methods described in section 5.5.3, the anticipated drug concentrations are expected to be detectable.

4.1.4 Drug assignment and administration of doses for each subject

This trial is a non-randomised, open-label, single arm, single period study. All subjects will receive both treatments, orally administered BI 409306 (T) as well as intravenously administered BI 409306 (C-13/N-15) (R). The treatments to be evaluated are outlined in Table 4.1.4; 1 below.

Table 4.1.4: 1 Dosage and treatment schedule

Treatment	Substance	Formulation	Unit strength	Dosage	Total dose
R (Reference)	BI 409306 (C-13/N-15)	i.v. solution	0.1 mg/mL	1 ml	0.1 mg
T (Test)	BI 409306	film-coated tablet	50 mg	50 mg single dose	50 mg

The oral medication will be administered as a single dose together with about 240 mL of water to a subject in the sitting or standing position under supervision of the investigating physician or an authorised designee.

During the first 2 h after oral drug administration, they are not allowed to lie down (i.e. no declination of the upper body of more than 45 degrees from upright posture).

The intravenous medication will be administered as a continuous intravenous infusion over 30 minutes under supervision of the investigating physician or an authorised designee. Start and end time of the infusion will be recorded.

The so-called four-eye principle (two-person rule) should be applied for administration of trial medication and – if applicable – its preparation, if correct dosage cannot be ensured

Proprietary confidential information © 2018 Boehringer Ingelheim International GmbH or one or more of its affiliated companies

otherwise. Administration will be performed following an overnight fast starting no later than 10 h before scheduled dosing.

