1	2	1	-1	-12:00	20:00	Admission to trial site ¹⁰	x ⁵					x
			-1:30	06:30	Allocation to treatment		x ²	x ²		x ²	x ²	x ²
			0:00	08:00	50 mg BI 409306 p.o.							
			0:10	08:10		x						
			0:20	08:20		x						x
			0:30	08:30	0.1 mg BI 409306 i.v.	x ⁸			▲			
			0:35	08:35			x					
			0:45	08:45		x	x					
			0:50	08:50			x					
			1:00	09:00		x ⁹	x ⁹		+			
			1:10	09:10			x					
			1:20	09:20		x	x			x	x ⁷	
			1:30	09:30			x					
			1:45	09:45		x	x					
			2:00	10:00	240 mL fluid intake	x	x			x	x	x
			2:30	10:30		x	x					
			3:00	11:00		x	x					
			3:30	11:30		x	x					
			4:00	12:00	240 mL fluid intake, thereafter lunch ³	x	x			x	x	
			5:00	13:00		x	x					
			6:00	14:00		x	x					
			7:00	15:00		x	x					
			8:00	16:00	Snack (voluntary) ³	x	x					
			9:00	17:00		x	x					
			10:00	18:00		x	x					
			11:00	19:00	Dinner						x	x
			12:00	20:00		x	x				x ⁷	
EOT	3	2	n.a.	n.a.	End of trial (EOT) examination ⁴	x ⁴				x ⁴	x ⁴	x ⁴

Proprietary confidential information © 2018 Boehringer Ingelheim International GmbH or one or more of its affiliated companies

1. Subject must be informed and written informed consent obtained prior to starting any screening procedures. Screening procedures includes physical examination, check of vital signs, ECG, safety laboratory (including drug screening), demographics (including determination of body height and weight, smoking status and alcohol history and pregnancy test in women), relevant medical history, concomitant therapy and review of inclusion/exclusion criteria. Pharmacogenetic samples will be collected if needed
2. The time is approximate; the procedure is to be performed and completed within 3 h prior to (oral) drug administration.
3. If several actions are indicated at the same time point, the intake of meals will be the last action.
4. End of trial examination includes physical examination, vital signs, ECG, safety laboratory including pregnancy test in women, recording of AEs and concomitant therapies

Date of EOT coincides with day 2 of visit 2. All EOT activities take place *after* the formal discharge from the trial site. Exception: blood for the EOT safety lab is taken in the context of the 24:00 hours post-dose sampling to avoid two separate punctures

5. Only urine drug screening and alcohol breath test, and pregnancy test in women.
6. AEs and concomitant therapies will be recorded throughout the trial, but will be specifically asked for at the time points indicated in the [Flow Chart](#) above.

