5.2.4 Electrocardiogram

Twelve-lead ECGs (I, II, III, aVR, aVL, aVF, V1 - V6) will be recorded using a computerised electrocardiograph (CardioSoft EKG System, GE Medical Systems, Freiburg, Germany) at the time points given in the [Flow Chart](#).

All ECGs will be recorded for a 10-sec duration after the subjects have rested for at least 5 min in a supine position. ECG assessment will always precede all other study procedures of the same time point (except blood drawing from an intravenous cannula which is already in place) to avoid impact of sampling on the ECG quality.

All ECGs will be stored electronically on the Muse CV Cardiology System (GE Medical Systems, Freiburg, Germany). Electrode placement will be performed according to the method of Wilson, Goldberger and Einthoven modified by Mason and Likar (hips and shoulders instead of ankles and wrists). All locally printed ECGs will be evaluated by the investigator or a designee. ECGs may be repeated for quality reasons (like alternating current artefacts, muscle movements, electrode dislocation) and the repeated ECG will be used for analysis. Additional (unscheduled) ECGs may be collected by the investigator for safety reasons.

Proprietary confidential information © 2018 Boehringer Ingelheim International GmbH or one or more of its affiliated companies

Abnormal findings will be reported as AEs (during the trial) or baseline conditions (at screening) if judged clinically relevant by the investigator. Any ECG abnormalities will be monitored carefully and, if necessary, the subject will be removed from the trial and will receive the appropriate medical treatment.

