5.2.5 Assessment of other safety parameters

5.2.5.1 Vital signs

Systolic and diastolic blood pressures (BP) as well as pulse rate (PR) will be measured by a blood pressure monitor (Dinamap Pro 100, GE Medical Systems, Freiburg, Germany) at the times indicated in the [Flow Chart](#), after subjects have rested for at least 5 min in a supine position. All recordings should be made using the same type of blood pressure recording instrument on the same arm if possible. Additional (unscheduled) BP data may be collected by the investigator for safety reasons. However, BP measurement on the arm where i.v. drug is administered must be avoided during the 30 min infusion period.

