6. INVESTIGATIONAL PLAN

6.1 VISIT SCHEDULE

Exact times of measurements outside the permitted time windows will be documented. The acceptable time windows for screening and end of trial examination are given in the [Flow Chart](#).

Study measurements and assessments scheduled to occur 'before' trial medication administration on Day 1 are to be performed and completed within a 3 h-period prior to the trial oral drug administration.

The acceptable deviation from the scheduled time for vital signs, ECG and laboratory tests will be \pm 30 min for the first 4 hours after oral drug administration and \pm 45 min thereafter.

If scheduled in the Flow Chart at the same time as a meal, blood sampling, vital signs and 12-lead ECG recordings have to be done first. Furthermore, if several measurements including venipuncture are scheduled for the same time, venipuncture should be the last of the measurements due to its inconvenience to the subject and possible influence on physiological parameters.

For planned individual plasma concentration sampling times refer to the Flow Chart. While these nominal times should be adhered to as closely as possible, the actual sampling times will be recorded and used for determination of pharmacokinetic parameter.

If a subject misses an appointment, it will be rescheduled if possible. The relevance of measurements outside the permitted time windows will be assessed no later than at the Blinded Report Planning Meeting.

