7.3.3 Safety analyses

Safety will be assessed for the endpoints listed in Section [5.2.1](#). All treated subjects (that is, all subjects who received at least one dose of study drug), will be included in the safety evaluation. Safety analyses will be descriptive in nature and will be based on BI standards.

The analyses will be done by 'treatment at onset'.

Treatments will be compared in a descriptive way. Tabulations of frequencies/proportions will be used for the evaluation of categorical (qualitative) data, and tabulations of descriptive statistics will be used to analyse continuous (quantitative) data.

Measurements (such as vital signs or laboratory parameters) or AEs will be assigned to treatments (see Section [4.1](#)) based on the actual treatment at the planned time of the measurement or on the recorded time of AE onset (concept of treatment emergent AEs).

Therefore, measurements planned or AEs recorded prior to first intake of trial medication will be assigned to 'screening', those between first trial medication intake until end of the residual effect period (see Section [5.2.2.2](#)) will be assigned to the treatment period. Events after the residual effect period but prior to next intake or end of trial examination will be summarized as 'follow-up'. These assignments including the corresponding time intervals will be defined in detail in the TSAP.

Adverse events will be coded using the Medical Dictionary for Regulatory Activities (MedDRA). Frequency, intensity and causal relationship of AEs will be tabulated by treatment, primary system organ class and preferred term. SAEs and other significant AEs (according to ICH E3), and AESIs will be listed separately (see Section [5.2.2.1](#)).

Proprietary confidential information © 2018 Boehringer Ingelheim International GmbH or one or more of its affiliated companies

Laboratory data will be compared to their reference ranges. Values outside the reference range will be flagged. Additionally, differences from baseline (screening measurements) will be evaluated.

For vital signs, the differences from baseline (last value before oral drug administration) will be evaluated.

Relevant ECG findings will be reported as AEs.

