7.8.3 Vital signs

Descriptive statistics over time and for the changes from baseline will be performed for vital signs (blood pressure and pulse rate) for both formulations together (BI tab + iv).

Section 7.3.3 of the CTP: *For vital signs, the differences from baseline (last value before oral drug administration) will be evaluated.*

In the listing the difference from baseline will also be displayed.

Clinically relevant findings in vital signs will be reported as AEs.

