7.8.4 ECG

ECG recordings will be checked by the investigator for pathological results. Clinically relevant abnormal findings for ECG will be listed under 'Relevant Medical History / Baseline Conditions' (when they occurred during screening) or will be reported as adverse events (when they occurred during treatment).

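### The ECG and vital signs at 1:20 h must be taken supine, but lying down is forbidden until 2:00 h after the oral dose, so no subject can follow both rules

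*Protocol*

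**What the plan says.** Five parts of the plan bear on this point.

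- **Protocol Flow Chart.** Time zero is the oral dose ("50 mg BI 409306 p.o"). The 1:20 h row (09:20) is marked for a 12-lead ECG and for vital signs, the latter with the footnote that adds local tolerability.
- **Protocol 4.1.4.** For the first 2 h after the oral dose, "they are not allowed to lie down (i.e. no declination of the upper body of more than 45 degrees from upright posture"). No exception is given for examinations.
- **Protocol 5.2.4 and 5.2.5.1.** ECGs are recorded "after the subjects have rested for at least 5 min in a supine position". Blood pressure and pulse are measured "after subjects have rested for at least 5 min in a supine position". Neither section offers another posture.
- **Protocol 6.1, repeated in SAP 6.7.** The permitted deviation for vital signs and ECG is ± "30 min for the first 4 hours after oral drug administration".
- **Analysis.** Protocol 7.3.3: "For vital signs, the differences from baseline (last value before oral drug administration) will be evaluated". SAP 7.8.3: "Descriptive statistics over time and for the changes from baseline will be performed for vital signs". For ECG, SAP 7.8.4 plans only a clinical check: "ECG recordings will be checked by the investigator for pathological results".

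**The concern.** The rules for posture, timing and measurement technique cannot all be met at 1:20 h. The site has three options, and each breaks one of them in every subject:

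1. Lie the subject down. This departs from the dosing condition in 4.1.4.
2. Measure seated or semi-recumbent. This departs from 5.2.4 and 5.2.5.1.
3. Wait until lying down is allowed. This misses the 6.1 window and moves the measurement into the slot of the 2:00 h set.

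The second option affects the data. The pre-dose baseline is supine, so a non-supine value at 1:20 h makes the change from baseline a mixture of posture and drug effect. This is the first post-dose vital-sign time point, 20 min after the scheduled end of infusion. Staff might also choose differently from subject to subject, because nothing in the plan says which rule takes precedence.

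For ECG no change from baseline is planned, so the issue there is only the built-in deviation.

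**Working it through.** The plan states no figure to reproduce. The check is clock arithmetic in minutes after the oral dose.

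**Inputs**

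- Scheduled time: 1:20 h = 80 min (Flow Chart)
- Window: ±30 min in the first 4 h (Protocol 6.1)
- End of the no-lying rule: 2:00 h = 120 min (Protocol 4.1.4)
- Minimum supine rest: 5 min (Protocol 5.2.4 and 5.2.5.1)

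**Does the Flow Chart really put both measurements at 1:20 h?** In the extracted table the post-dose PK marks are displaced by a column. The ECG and vital-sign marks in the 1:20 h row, however, sit in the same two positions as in the pre-dose, 2:00 h and 4:00 h rows. The local-tolerability footnote also fits the vital-sign column. The reading is consistent.

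**Window for the 1:20 h set**

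- Opens: 80 − 30 = 50 min (0:50)
- Closes: 80 + 30 = 110 min (1:50)
- Gap to the end of the restriction: 120 − 110 = 10 min

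The whole window lies inside the restricted period.

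**Earliest measurement that meets both posture rules**

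- 120 + 5 = 125 min (2:05)
- After the nominal time: 125 − 80 = 45 min
- After the window closes: 125 − 110 = 15 min

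**Other time points**

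| Set | Window | Can a supine measurement comply? |
|---|---|---|
| 1:20 h | 0:50 to 1:50 | No |
| 2:00 h | 1:30 to 2:30 | Yes, from 2:05 to 2:30 |
| 4:00 h | 3:30 to 4:30 | Yes |

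**Could supine be read as semi-recumbent?** Section 4.1.4 treats any recline beyond 45 degrees from upright as lying down. A position that satisfies 4.1.4 is therefore at most halfway back from upright and cannot reasonably be called supine.

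**Extent.** As the Flow Chart columns read, 1:20 h is 1 of 3 post-dose ECG rows on Day 1 (1:20, 2:00, 4:00) and 1 of 5 post-dose vital-sign rows (1:20, 2:00, 4:00, 11:00, 12:00).

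**The case against.** The strongest reply is that the conflict is a wording gap with little consequence. Sections 5.2.4 and 5.2.5.1 are the specific instructions for the procedure, so staff would naturally apply them and lay the subject down briefly. All values would then be supine and SAP 7.8.3 would be unaffected. Safety data are descriptive only, in a single arm of up to 12 subjects. SAP 6.2 would class the resulting deviation as non-important, and Protocol 6.1 already has out-of-window measurements documented and assessed.

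Much of this stands. The damage to blood pressure and pulse data is conditional on staff keeping the posture restriction, and the documents do not show which way they would go. It does not remove the contradiction, because the precedence of the specific instruction is nowhere written. Even on the favourable reading, every subject departs from 4.1.4. Each such deviation must still be assessed under SAP 6.2.

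A second objection is that the exception has a cost: supine time soon after an oral dose, in a trial about oral absorption. That is fair, and the time is greater if subjects also rest supine before 2:00 h for the 2:00 h set. The amount is small and is set out with the fix.

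**Conclusion.** The point holds. As written, the ECG and vital signs at 1:20 h cannot be done in compliance with 4.1.4, 5.2.4, 5.2.5.1 and 6.1 together, in any subject. It is an internal inconsistency confined to one time point, and the only planned analysis exposed is the descriptive change from baseline in blood pressure and pulse.

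The deviation itself is certain. The mixing of posture with drug effect arises only if the 1:20 h values are taken non-supine. The conclusion rests on the Flow Chart columns being read as above and on supine meaning a recline of more than 45 degrees from upright. The primary PK analysis is not shown to be affected. The correction is worth making because it is simple and applies to every subject.

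**What to change.** Add to Protocol 4.1.4, after the restriction on lying down: *except for the brief supine rest needed for scheduled ECG and vital-sign measurements*. Baseline and all post-dose values are then supine, and 5.2.4, 5.2.5.1 and SAP 7.8.3 need no change.

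The cost is one clause in an amendment, no extra procedure, and a few supine minutes before 2:00 h. Assuming 5 to 10 min in total, that is 5/120 = 4.2% to 10/120 = 8.3% of the restricted period. If the 2:00 h set is also rested for before 2:00 h, the two rests alone take 5 + 5 = 10 min, and recording time at 1:20 h comes on top. Taking the 2:00 h set between 2:05 and 2:30, which its window allows, avoids the second rest.

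If the sponsor wants no supine time before 2:00 h, the alternative is to specify in 5.2.4 and 5.2.5.1 one semi-recumbent posture, no more than 45 degrees from upright, for baseline and all post-dose ECG and vital-sign measurements. That also keeps posture constant, but it changes the measurement posture at every time point to resolve a conflict at one, so the exception in 4.1.4 is preferable.

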4.1.5 Blinding and procedures for unblinding

No blinding was performed because the treatments are distinguishable from each other. This Phase I trial will be handled in an open fashion throughout (that is, during the conduct, including data cleaning and preparation of the analysis). This is considered acceptable because the potential for bias seems to be low and does not outweigh practical considerations.

Emergency envelopes will not be provided, since all subjects receive the same dose of different formulations in an open label design.

4.1.6 Packaging, labelling, and re-supply

Drug supplies will be provided by the Department of Pharmaceutical Development of Boehringer Ingelheim Pharma GmbH & Co. KG, Biberach, Germany.

The clinical trial supply consists of containers holding the trial medication which are labeled with trial identification. The required information according to the German Drug Law as well as Annex 13/EU GMP Guideline will be provided on the containers. The clinical trial supply containers will be labeled with:

- BI trial number
- Name of product and strengths or identification code
- Pharmaceutical dosage form, quantity of dosage units
- Route and mode of administration
- Term 'For Clinical Trial Use' (domestic language)
- Sponsor name and address
- Storage conditions
- Use-by date
- Batch number

The telephone number of the sponsor and name, address and telephone number of the trial site are given in the subject information form. The EudraCT number is indicated on the title page of this protocol as well as on the subject information and informed consent forms. Examples of the labels will be available in the ISF.

No re-supply is planned.

4.1.7 Storage conditions

Drug supplies will be kept in their original packaging and in a secure limited access storage area according to the recommended (labeled) storage conditions. Where necessary, a temperature log must be maintained to make certain that the drug supplies are stored at the correct temperature. If the storage conditions are found to be outside the specified range, the local clinical monitor (as provided in the list of contacts) is to be immediately contacted.

4.1.8 Drug accountability

The investigator will receive the investigational drugs delivered by the sponsor when the following requirements are fulfilled:

- Approval of the trial protocol by the IRB / ethics committee
- Approval/notification of the regulatory authority, e.g. competent authority
- Availability of the curriculum vitae of the principal investigator
- Availability of a signed and dated clinical trial protocol

Only authorised personnel as documented in the form 'Trial Staff List' may dispense medication to trial subjects. The trial medication must be administered in the manner specified in the CTP. All unused medication will be disposed locally by the trial site upon written authorisation by the clinical monitor. Receipt, usage and disposal must be documented on the respective forms. Account must be given for any discrepancies.

The investigator must maintain records of the product's delivery to the trial site, the inventory at the site, the use by each subject, and the disposal of unused products.

These records will include dates, quantities, batch / serial numbers, expiry ('use-by') dates, and the unique code numbers assigned to the investigational products and trial subjects. The investigator will maintain records that document adequately that the subjects were provided the doses specified by the CTP, and that reconcile all investigational products received from the sponsor. At the time of disposal, the investigator must verify that all unused or partially used drug supplies have been returned by the clinical trial subject and that no remaining supplies are in the investigator's possession.

4.2 OTHER TREATMENTS, EMERGENCY PROCEDURES, RESTRICTIONS

4.2.1 Other treatments and emergency procedures

There are no special emergency procedures to be followed. No additional treatment is planned. However, in case of adverse events in need of treatment, the investigator can authorise symptomatic therapy. In those cases, subjects will be treated as necessary and, if required, kept under supervision at the trial site or transferred to a hospital until all medical evaluation results have returned to an acceptable level.

4.2.2 Restrictions

4.2.2.1 Restrictions regarding concomitant treatment

In principle, no concomitant therapy is allowed. All concomitant or rescue therapies will be recorded (including time of intake on study days) on the appropriate pages of the CRF. CYP2C19 or 1A2 inhibitors or inducers are not allowed due to their interaction potential with BI 409306. Acetylsalicylic acid is not allowed due to potential for CYP2C19 induction. Ibuprofen may be used as analgesic drug if need be.

